Outcomes will be assessed by interview but in addition (to assess potential bias due to ineffective blinding of interviewers) self-completed questionnaires will be completed by a randomly selected 50% of surviving subjects at 6 months and by the other 50% at 12 months. The primary outcome will be functional health status as measured using the Nottingham Extended ADL scale¹³. All outcomes will be measured at base line and at 3, 6 and 12 months after recruitment by interviewers who are unaware of the treatment allocation (see below). Carer interviews will take place within 1 month of patient interviews. Secondary outcome measures will include survival (death certifications) and changes in subject's perceived mental state (Hospital Anxiety and Depression Scale⁽¹⁴⁾), change in household or residential or nursing home circumstances (study records), informal caregiver's psychological health (General Health Questionnaire (GHQ)⁽¹⁵⁾) and patient's and informal caregiver's views of 'treatment' (semi-structured interviews). Therapy Outcome Measures (TOMS) will be used to measure outcomes in relation to rehabilitation aims.

Assessment of quality of life is implicit within the choice of outcome measures, (including EuroQOL). No generic and comprehensive quality of life measure is proposed since there is no evidence that a suitable measure exists for this particular patient group. Taken together the proposed outcome measures cover the traditional domains of quality of life included in generic measures. In the absence of reliable patient reported data, data collected from informal caregivers will be substituted where appropriate since previous studies have indicated that informants are a source of reliable data^(16 17 18). The applicants have used all the proposed outcome measures identified in recent studies and found them to be appropriate to the study.

Patient Interviews

Patients will be interviewed in their own homes, following prior arrangement by telephone or letter, by a researcher unaware of their treatment allocation. The interviews have been shown in the pilot to take between 30 minutes to an hour. Patients' welfare will be considered of paramount importance at all times. Proxy information will be used if the interviewer feels that the patient is not capable of answering questions accurately. This will be judged by a combination of AMT score and ability to answer pre-interview questions. The interview will

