A Cost consequences analysis and a Cost-effectiveness analysis (which will become a Cost minimisation analysis if no significant difference in costs will be found) will be conducted. In Cost consequences analysis all the outcome results from the clinical study will be listed and will not combined with the (incremental) costs. In Cost effectiveness analysis the benefits will be measured in terms of the primary clinical outcome (functional ability score measured by the Nottingham EADL scale). Patients included in the study sample will be comparable in terms of clinical and prognostic features across sub-samples.

We are aware that the use of specific-condition health status measures in economic evaluations has some limitations, given the assumption of no interactions between dimensions. Alongside the specific-condition health status measure, a generic validated instrument which allows to combine different aspects of health status will be adopted (EQ-5D). We will investigate the nature of the correlation within and between instruments.

Resource data collection and costing methods

The use of health and social services will be monitored and costed. These services will include not only the therapy and direct costs related to the rehabilitative interventions ('packages of care') under investigation, but also those related to any subsequent use of health care and social services. Any difference in carers' use of time will also be considered. Estimation of resources included in 'packages of care': It is expected that day hospital interventions will vary within and between centres. The contents and quantities of service inputs used in relation to the packages of care delivered in day-hospital (local geriatric day hospital service) or at home (own home or residential and nursing homes) will not be established by rigid protocols within the study. The present trial is in fact pragmatic; moreover, we think it may not be practically feasible to obtain health care professionals' compliance to the protocols, given the nature of the interventions and actual variety of care.

The contents of the packages of care and their measurements will therefore be assessed by observation. Data will be collected prospectively for each patient in each centre. Pro-formas for data collection will be completed by the NHS staff. The final aim is to estimate a cost per patient day in both DHR and HBR, in relation to the provision of physiotherapy, occupational

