	Reliability	Validity	Appropriate to population
HADS	Zigmond and Snaith (1983) Bjelland et al (2002)	Zigmond and Snaith (1983) Bjelland et al (2002)	Bjelland et al (2002) Wolf et al (2001)
GHQ	Bowling (1995)	(Bowling 1995)	Watts et al (2002) Bautz-Holter et al (2002)
NEADL	Bowling (1995)	I-Ping (2000)	Harwood et al (2002), Nichol et al (2002)
EUROQUOL	Schrag et al (2000)	Schrag et al (2000)	Wade et al (2003)

Economic Questionnaire for patients

University of Sheffield Sheffield Institute for Studies on Ageing Rehabilitation of Older Patients: day hospital compared to rehabilitation at home – HTA Project No: 97/26/01		
Patient Interview Schedule 2 – Economic		
Patient study number		1
Interviewer ([name]=1)		2
Interview done in home(1)/hospital(2)		3
Date		4
Baseline(0)/3 months (1)/6 months(2)/1 year(3)		5
Proxy? Yes(1)/No(2)		6
Relationship of proxy to patient Husband/wife (1) Son/daughter (2) Grandchild (3) Other relative (4) Friend (5) Paid carer (6)		7
0	So, when did you start your rehabilitative treatment (date)?	8
	Now I will ask you a series of questions about the use of health and social services through the NHS. I only want to know about things you have had in addition to your rehabilitation treatment:	
1	In the last 8 weeks have you done any of the following because of your condition or other health reasons? Can you please also remember how many times these events have happened? Please do not count visits you have made as part of your rehabilitation treatment.	
a)	Have you been seen by the family doctor or another GP at a doctor's surgery?	9
	Yes..... 1 no. times  	10

	No 2	
b)	Have you been seen by a nurse at a surgery? Yes 1 no. times   No 2	11 12
c)	a) Did you or anyone else speak to a nurse from a doctor's surgery about you on the telephone? Yes 1 no. times   No 2	13 14
d)	Did you or anyone else speak to a doctor at the surgery about you on the telephone? Yes 1 no. times   No 2	15 16
e)	Did you or anyone else telephone NHS Direct? Yes 1 no. times   No 2	17 18
f)	Have you visited an emergency doctor at an "out of hours" clinic? Yes 1 no. times   No 2	19 20

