16	Because of your condition or other health reasons have you had to either rent new accommodation or sell your house since in the last 8 weeks? Yes (1) No (2) If no skip to question 19	291
17	Has this caused a financial loss to you or your family? Yes (1) No (2) If yes how much was the loss? £.....	292 293
18	How much did it cost you to move your furniture and personal things? £.....	294
19	In the last 8 weeks, have you moved into residential/nursing home or made use of day care centres/sitting services at home because of your condition or other health reasons? Yes (1) No (2) If no skip to question 22	295
	How many days in the last 2 months? Permanently	296
	Short stay	297
	Day care centre	298
	Sitting services	299
20	Do you pay personally for you to stay in residential/nursing care or make use of day care centre/sitting services? Yes (1) No (2) If no, who pays?.....	300
21	How much are your bills monthly? £.....	301

22	In the last 8 weeks, did you have to meet any travel costs because of your condition or other health reasons (e.g. to attend clinical appointments, or to get the prescribed treatment/equipment)? Yes (1) No (2) If no skip to question 26	302
23	Can you please provide as much information as you can about the travel	

ts you had to meet because of your condition or other health reasons? ease include costs for return journeys).
														

Can you tell me how you travelled?
 
Tick=1 No tick=2
	
Please tick all that apply.
	
How many miles did you travel overall
 
(If you can't remember exactly, can you please estimate it)
												
		
How much did these journeys cost you altogether?
 
(If you can't remember exactly, can you please estimate it)
												
		
 
 £	p	
 
 		
 
 		
 
 		
 
 		
 
 		
 
	£	p										
£	p													
By train/metro														
By bus														
By private car														
By taxi														
		303 304 305												
		306 307 308												
		309 310 311												
		312 313 314												
24	
If you travelled by car, did you have to pay any tolls or parking fees?
 
Yes (1) No (2)
 
If no skip to question 26
	315												
25	
How much did you pay for tolls or parking fees?
 
£.....
	316												

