32	Who do you live with at home? 
 With your husband/wife or a partner 1 With your children 2 With your parents 3 With a brother or sister 4 With some other person 5 No one - I live alone 6 
	338
33	Are you: 
 Married or living with a partner 1 Divorced or separated 2 Widowed 3 Single 4 
	339
34	Are you or your family members currently receiving any of the following allowances? 
 Jobseeker's allowance (Ex-Unemployment benefit) 01 Income support 02 Working tax credit (Ex-working families tax credit) 03 Statutory sick pay 04 Incapacity benefit (Ex-Invalidity benefit) 05 Severe disablement allowance 06 Health benefits 07 Attendance allowance 08 Carers allowance (Ex-Invalid care allowance) 09 Council tax benefit 10 Housing benefit 11 Disability living/allowance 12 State retirement pension 13 Disabled persons tax credit 14 Other (Please write in what) 15 Not receiving any 16 
	340 341 342 343 345 346 347 348 349 350
35	What is your date of birth?	351
36	(Record gender of patient). Male (1) Female (2)	352

Carer questionnaire

University of Sheffield Sheffield Institute for Studies on Ageing Rehabilitation of Older Patients: day hospital compared to rehabilitation at home – HTA Project No: 97/26/01	
Carer Interview Schedule	
Patient study number	1
Interviewer ([name]=1)	2
Interview done in home(1)/hospital(2)	3
Date	4
Baseline(0)/3 months (1)/6 months(2)/1 year(3)	5

1	So, when did you start to assist Mr/Mrs (Patients name)	6
2	What is your relationship to the person you are assisting? Are you: 
 His/her spouse/partner 1 His/her child 2 His/her grandchild 3 A friend 4 A paid carer 5 Other (please write in relationship) 6 
	7

3	
Which of the following best describes your current position about work? (Please ring one number only).
 
Full or part time 1 Retired 2 At home and not looking for paid employment 3 (eg looking after your home, family or other dependants) Unable to work due to illness or disability 4 Unemployed and looking for work 5 Other (please write in) 6
 
.....
	8

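### Q19 of the patient economic questionnaire asks about moving into a care home, not living in one, so established residents skip the permanent-care days and cost items

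*Protocol*

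**What the plan says.** **Source of the cost data.** In the Protocol's economic evaluation, Resource data collection and costing methods lists permanent care among the services to be monitored by questionnaire in both groups. Extraction from patients' records is described only for procedures and investigations in hospital. Data on all other services are to come from patient interviews. Table 5 places residential-care costs in the patient economic questionnaire.

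**Who can be a resident.** The same section describes care delivered "at home (own home or residential and nursing homes"), and the inclusion criteria keep exclusions to a minimum. A care-home resident can therefore be in the trial.

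**The items on the printed form (Economic Questionnaire for patients).**
- Q19, with an 8-week look-back, asks "have you moved into residential/nursing home or made use of day care centres/sitting services at home because of your condition" or for other health reasons. Its instruction is "If no skip to question 22".
- Behind that filter are "How many days in the last 2 months" (split into permanent, short stay, day centre and sitting service), Q20 on who pays, and Q21, "How much are your bills monthly".
- Q32, "Who do you live with at home", offers spouse or partner, children, parents, sibling, some other person, or no one.
- The place of interview is coded "Interview done in home(1)/hospital(2").

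**The related secondary outcome.** Outcome measures names "change in household or residential or nursing home circumstances (study records"). The source given is study records, not this questionnaire.

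**The concern.** Q19 asks about an event, a move within the last 8 weeks. The cost of permanent care depends on a state, namely being resident during the period costed. The two agree only at an interview held within 8 weeks of the move. At every later interview, a settled resident who answers literally says No and passes over the fields meant for them.

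That No is also the answer of a patient who has never been in care. No other item shown separates the two. A resident has no fitting code at Q32. Place of interview is only home or hospital. Q16, on renting or selling a home, is again limited to events in the last 8 weeks.

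What is at stake is the cost comparison. That home-based rehabilitation is less costly is one of the trial's hypotheses, and permanent care is a continuing cost that the plan says it will count. If one setting delays care-home entry, the part of the cost difference due to permanent care would be under-recorded.

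**Working it through.** The plan gives no figure to reproduce. The check applies Q19's wording and skip rule to the interview timetable.

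**Inputs**
- Interviews: baseline, 3, 6 and 12 months (form header; Outcome measures), taken as weeks 0, 13, 26 and 52.
- Look-back at Q19: 8 weeks = 56 days (printed form).
- Skip rule: No goes to Q22 (printed form).
- Assumptions: residence continues once begun, the patient uses no day care or sitting service, and the question is answered as worded.

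**Step 1. Moves that Q19 can see.** The window at each interview runs from 8 weeks before it:
- 3 months: 13 − 8 = 5, so weeks 5 to 13
- 6 months: 26 − 8 = 18, so weeks 18 to 26
- 12 months: 52 − 8 = 44, so weeks 44 to 52

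Together these cover 3 × 8 = 24 of 52 weeks (46%). The gaps are weeks 0 to 5, 13 to 18 and 26 to 44, in all 5 + 5 + 18 = 28 weeks (54%). The largest is weeks 26 to 44.

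**Step 2. Entry in the largest gap, for example week 30.** The 6-month interview precedes the move. At 12 months the move was 22 weeks ago, so the answer is No and the days field is skipped. The patient was resident for all 56 days asked about. Recorded stay is none. A status question with the same 8-week window would record 8 weeks.

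**Step 3. Resident since before baseline.** The answer is No at 3, 6 and 12 months. A move in the 8 weeks before baseline gives a Yes at the baseline interview only. Recorded follow-up stay is none. A status question would record 3 × 8 = 24 weeks.

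**Step 4. Entry at week 20, separating the two causes.**

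| | Weeks |
|---|---|
| True stay to week 52 (52 − 20) | 32 |
| Recorded at 6 months (26 − 20) | 6 |
| Recorded at 12 months with Q19 as printed | none |
| Recordable with a status question, same window (6 + 8) | 14 |

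The shortfall is 32 − 6 = 26 weeks. Q19's wording explains 14 − 6 = 8 of these (8/26 = 31%). The other 18 weeks (weeks 26 to 44) lie outside any 8-week window and would be missed even with a status question.

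**Step 5. Sensitivity to the timetable.** The economic section gives interviews at 1, 3, 6 and 12 months. An added 1-month interview raises coverage to 28.3 of 52.2 weeks (54%) and leaves the gap from week 26 to 44 unchanged. That section also speaks of the previous month, where the form says 8 weeks. With one-month recall, coverage falls to 13.0 of 52.2 weeks (25%) on the 3, 6 and 12 month schedule, or 17.4 of 52.2 (33%) with the 1-month interview.

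**The case against.** **The block was evidently meant to capture stay.** It has a field for permanent days, Q20 asks about paying for a stay, and the interviewers are trained. A sensible interviewer might enter Yes for a resident. That is fair, and a No is what the literal wording produces, not a certainty. But these fields all sit behind the filter, and nothing printed tells the interviewer to depart from it.

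**A permanent stay recorded once can be carried forward.** This could rescue the week-20 case. It cannot rescue patients whose move fell in a gap or who were resident before baseline and were never recorded.

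**Randomisation balances the loss.** In expectation it does so for patients resident at baseline. It does not for entries after randomisation if the setting affects them.

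**Three stronger readings should be resisted.**
- A reader might infer that the secondary outcome on residential circumstances goes unrecorded. The documents do not support this. Its source is study records, which are not reproduced, and a patient resident throughout has no change to record in any case.
- A reader might infer that residents are entered as zero days and zero cost. The form leaves those fields blank, and no rule costs blanks as nil. What stands is that the form gives an analyst no means of telling a resident's blank from that of someone never in care.
- A reader might take 6 of 32 weeks (19%) as the effect of Q19's wording. That figure mixes the wording with the length of the recall window.

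**Conclusion.** The point holds for the costing of permanent care. Followed as printed, Q19 to Q21 miss all follow-up stay for residents since before baseline and for patients entering care between about weeks 26 and 44. For a patient entering at week 20, the wording lowers recorded stay from 14 weeks to 6. Because the protocol describes no other source for this cost, the gap bears directly on the cost hypothesis.

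This rests on literal answers, continuous residence and no use of day care or sitting services, since such use would turn Q19 to Yes. The effect on the between-group cost difference cannot be sized, because the protocol gives neither the share of residents at entry nor a rate of care-home admission. No conclusion is drawn about the secondary outcome.

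**What to change.** 1. Reword Q19 as a status question, for example: in the last 8 weeks, have you lived or stayed in a residential or nursing home? Current residents then complete the days items and Q20 to Q21 whenever they moved in.
2. Ask about day-care centres and sitting services in a separate question, so that a Yes has one meaning.
3. Add residential-home and nursing-home codes and a date of entry to Q32, at baseline and every follow-up interview. For continuous stays, the date also lets the weeks between recall windows be derived, which rewording Q19 alone does not (the 18 weeks in the week-20 example).

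The cost is a few extra response fields and some renumbering, on an interview already held, with no extra visit. Entry dates may need a proxy for some patients, for which the form already provides.
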